SUMMARY

Rationale:

Patients undergoing major noncardiac surgery may experience major adverse postoperative events (MAPE), which lead to mortality and morbidity. Such complications are hard to diagnose, as typical symptoms are often not present in most often postoperative patients (e.g., chest pain may be masked by pain medication).

Routinely measuring cardiac troponins during the perioperative period is an accurate method to confirm diagnosis of postoperative myocardial injury (PMI). In patients aged > 60 years undergoing intermediate or high risk noncardiac surgery, PMI occurs in 15% of the patients. Approximately one third of them develops an often symptomless myocardial infarction. However, PMI is also associated with other cardiac and noncardiac pathologies including heart failure, arrhythmias, pulmonary embolism, sepsis and renal failure. Therefore, we consider PMI as either myocardial infarction or noninfarct troponin elevation (NITE). Currently, the etiology and long term effects of PMI on disability are unknown. Differentiation of patients with PMI in the appropriate disease entity will hopefully contribute to more suitable treatment and prevention of major complications.

The aim of this study is to investigate and compare the independent prognostic effects of the different PMI phenotypes (myocardial infarction and NITE) and noncardiac MAPE on disability. We will be diagnosing the differing PMI phenotypes using clinical evaluation and biomarkers.

Objective:

Primary objective

To investigate and compare the independent prognostic effects of the different PMI phenotypes (myocardial infarction and NITE) and noncardiac MAPE on disability in patients undergoing elective noncardiac surgery.

Secondary objectives

1. To investigate and compare the independent prognostic effect of the different PMI phenotypes (myocardial infarction and NITE) and noncardiac MAPE on disability free survival in patients undergoing elective noncardiac surgery.
2. To examine whether (combinations of) perioperatively measured biomarkers are associated with in-hospital MAPE in patients undergoing elective noncardiac surgery. MAPE are divided in different subtypes, including:
 - a. MACE, which is defined as the composite endpoint of cardiovascular death, non-fatal myocardial infarction, non-fatal cardiac arrest, non-fatal ventricular fibrillation,

ventricular hemodynamic compromise, atrial fibrillation requiring cardioversion, pulmonary embolism and stroke.

- b. Noncardiac MAPE including sepsis, renal failure, unexpected intensive care unit (ICU) admission and respiratory disorders.
- c. All-cause mortality

3. To examine whether (combinations of) perioperatively measured biomarkers are associated with 6-month MACE and all-cause mortality in patients undergoing elective noncardiac surgery.
4. To assess the added value of the perioperatively measured biomarkers on top of the currently used Revised Cardiac Risk Index (RCRI) to predict MACE after noncardiac surgery.

Study design

This prospective observational cohort study includes patients, aged 60 years and older, undergoing elective intermediate or high risk noncardiac surgery under spinal or general anesthesia with an expected postoperative hospital admittance of at least 24h. All patients are required to visit the preanesthesia outpatient clinic for preoperative consultation. In addition to care as usual, extra blood samples will be taken preoperatively and postoperatively up to three days after surgery to determine the following biomarkers: high sensitive troponin, brain natriuretic protein, C-reactive protein, creatinine and hemoglobin. At postoperative day 2, extra to routine care noninvasive imaging (i.e. electrocardiography and transthoracic echography) will be performed. Preoperatively measured biomarkers are considered baseline measurements. Biomarker values will be blinded from treating physicians in case this particular biomarker was not measured in routine care. In-hospital MAPE will be monitored including cardiac events, respiratory failure, pulmonary embolism, sepsis, renal failure and mortality. In addition, patients will be asked to fill out the WHODAS 2.0 questionnaire preoperatively and 6 months after their surgery to assess disability. Their general practitioners (GPs) will be approached to determine whether MACE and/or mortality have occurred during the 6 months follow up after surgery.

Study population

Patients aged >60 years undergoing elective intermediate (e.g. hip replacement) or high risk (e.g. liver resection) noncardiac surgery under general or spinal anesthesia with a postoperative hospital stay of at least 24 hours are eligible for participation in this study. We aim to include 500 patients in this study. Approximately 1,200 patients undergo elective major noncardiac surgery each year in the UMC Utrecht. Taking into account nonparticipation and potential lower inclusion rates at the

beginning of the study, the estimated inclusion time is one year with six months follow-up resulting in a total study time of 18 months.

Main study parameters/endpoints:**Primary end points:**

Disability is expressed in terms of the WHODAS 2.0 which is based on different functional domains, including cognition, mobility, self-care, getting along, life activities and participation.

Secondary endpoints:

- *Disability free survival* is defined as being alive with a WHODAS 2.0 score $\leq 25\%$ and no increase of the preoperative score $\geq 25\%$ at 6 months after surgery.
- *An in-hospital major adverse postoperative events (MAPE)*, which could be distinguished in:
 - o *Major adverse cardiac event (MACE)*, which is defined as the composite endpoint of cardiovascular death, non-fatal myocardial infarction, non-fatal cardiac arrest, non-fatal ventricular fibrillation, non-fatal ventricular hemodynamic compromise and atrial fibrillation requiring cardioversion.
 - o *Noncardiac MAPE*, which is defined as a composite outcome consisting of respiratory disorders (including pneumonia and respiratory failure), pulmonary embolism, sepsis and/or systemic inflammatory response syndrome (SIRS), renal failure, reoperation and unplanned ICU admission.
- *In hospital all-cause mortality*
- *Length of hospital stay*
- *6-month MACE*
- *6-month all-cause mortality*

Nature and extent of the burden and risks associated with participation, benefit and group**relatedness:**

In addition to routine care, patients will be asked to fill out the WHODAS 2.0 before surgery and additional blood will be drawn (7 cc in total) before induction of anesthesia. Postoperatively, extra blood will be taken up to three days after surgery (7 cc in total each time) during routine blood draws. At postoperative day 2, an electrocardiogram (ECG) and transthoracic echo (TTE) will be performed. Six months after surgery, patients will be asked to fill out the WHODAS 2.0 for the second time and their GPs will be approached to assess whether clinically relevant events have occurred. The study is associated with a negligible risk as only noninvasive imaging procedures will be performed

and blood will be drawn. The treating physician will be notified in case any unexpected findings from the ECG and TTE are observed meaning that participation to this study could lead to early recognition of heart disease.

1. INTRODUCTION AND RATIONALE

Worldwide, over 300 million patients undergo major noncardiac surgery every year¹ and this number has been increasing continuously². Despite the beneficial aspects of surgery, approximately 19% of these patients will suffer an in-hospital major adverse postoperative event (MAPE)³. The most common MAPE had an infectious (33%) or cardiovascular origin (19%) with highest mortality rates observed in patients with a major adverse cardiac event (7.0%)³. Major adverse cardiac events (MACE) are a leading cause of postoperative morbidity and mortality⁴⁻⁷ and is associated with prolonged hospitalization and increased medical costs⁸.

function, in patients with PMI and thereby, patients will be treated more appropriately and major complications could (hopefully) be prevented.

Nowadays, the Revised Cardiac Risk index (RCRI) is commonly used as a predictive tool to estimate the probability of MACE or mortality¹³. The RCRI includes six predictors, which are high risk surgery, history of myocardial infarction (MI), history of cerebrovascular disease, chronic heart failure, elevated creatinine and insulin dependent diabetes. Ford et al. performed a review on the performance of the RCRI in several validation studies and found that this cardiac index only moderately predicts, does not predict events in vascular surgery, and has not been prospectively validated using troponin or other biomarkers to predict MI or other cardiac events¹⁴. Since this publication, several studies reported the added predictive value to the RCRI of one (or more) biomarker(s), including (high sensitive) troponin¹⁵⁻¹⁷, (NT-pro)BNP^{15,16,18-20}, eGFR^{21,22}, CRP^{18,20}, ECG^{23,24} and transthoracic echocardiography^{19,25}. Addition of (high sensitive) troponin, (NT-pro)BNP and/or CRP to the RCRI seems promising for the prediction of MACE as the predictive performance significantly improves compared to the RCRI by itself. To our knowledge, different combinations of several biomarkers together in addition to the RCRI have not been reported yet.

Our primary objective is to investigate and compare the independent prognostic effect of the different PMI phenotypes (myocardial infarction and NITE) and noncardiac MAPE on disability. We will be diagnosing the differing PMI phenotypes using clinical evaluation and biomarkers. The primary endpoint is disability. Disability is assessed using the World Health Organization Disability Assessment Score 2.0 (WHODAS 2.0)²⁶. Our primary hypothesis is that any postoperative troponin elevation regardless of its association with MACE or noncardiac MAPE is independently associated with an increased risk of death and disability.

2. OBJECTIVES

2.1 Primary objective

To investigate and compare the independent prognostic effect of the different PMI phenotypes (myocardial infarction and NITE) and noncardiac MAPE on disability in patients undergoing elective noncardiac surgery.

2.2 Secondary objectives

1. To investigate and compare the independent prognostic effect of the different PMI phenotypes (myocardial infarction and NITE) and noncardiac MAPE on disability free survival in patients undergoing elective noncardiac surgery.
2. To examine whether (combinations of) perioperatively measured cardiac biomarkers are associated with in-hospital major adverse postoperative events (MAPE) in patients undergoing elective noncardiac surgery. MAPE are divided in different subtypes, including:
 - a. Major adverse cardiovascular events (MACE), which is defined as the composite endpoint of cardiovascular death, non-fatal myocardial infarction, non-fatal cardiac arrest, non-fatal ventricular fibrillation, ventricular hemodynamic compromise, atrial fibrillation requiring cardioversion, pulmonary embolism and stroke.
 - b. Noncardiac major adverse postoperative events (MAPE) including sepsis, renal failure, unexpected ICU admission and respiratory failure.
 - c. All-cause mortality
3. To examine whether (combinations of) perioperatively measured cardiac biomarkers are associated with 6-month MACE and all-cause mortality in patients undergoing elective noncardiac surgery.
4. To assess the added value of the perioperatively measured biomarkers on top of the currently used Revised Cardiac Risk Index (RCRI) to predict major adverse cardiac events (MACE) after noncardiac surgery.

[figure not shown]
3. STUDY DESIGN

This prospective observational cohort study includes patients undergoing major elective noncardiac surgery. Major elective noncardiac surgery is defined as all surgical procedures under spinal or general anesthesia with a postoperative hospital admittance of at least 24 hours that have been preceded by a preoperative consultation at the preanesthesia outpatient clinic. Patients are treated at the University Medical Center Utrecht (UMCU).

Each year, approximately 1,200 patients undergo major noncardiac surgery at the UMCU. We intend to include 500 patients in this study. Taking non-participation into account and lower inclusion rate at the initial study phase, the expected duration of inclusion will be one year with a 6 month follow up leading to a total study period of 18 months.

In figure 1, an overview of the proposed study procedures is shown. In short, patients visit the preanesthesia outpatient clinic for preoperative consultation and will be asked to participate in our study. Standard diagnostic tests, such as ECG, will be performed based on local protocol or additional diagnostic tests or markers are requested at the discretion of the screening anesthesiologist. One week before surgery, patients will be approached by telephone and asked if they are interested in participation in our study. In case patients are willing to participate, the WHODAS 2.0 questionnaire is taken off by the researcher. Informed consent will be signed at the day of hospital admission before surgery. Extra blood will be drawn before induction of anesthesia and stored for biobanking. Postoperatively, blood samples will be drawn at postoperative days 1-3. At postoperative day 2, additional imaging (i.e. ECG and TTE) will be performed. In addition, in-hospital clinical relevant outcomes, including MACE and major noncardiac events, will be monitored. Patients are followed up until 6 months after surgery by sending them the WHODAS 2.0 and a questionnaire regarding the clinical relevant events (i.e. MACE and mortality) since the date of the surgery. Patients will be contacted by the researcher to take off the questionnaires by telephone. In addition, their general practitioners will be approached to ask similar questions regarding the patients' clinically relevant events during these 6 months follow up to verify details of the events.

Figure 1. Flowchart of proposed study procedures

ECG: electrocardiography; creat: creatinine; Hb: hemoglobin, TTE: transthoracic echocardiography, WHODAS 2.0: 12-item World Health Organization Disability Assessment Score 2.0; hsTroponin: high sensitive troponin; BNP: brain natriuretic peptide; CRP: C-reactive protein; GP: general practitioner.

4. STUDY POPULATION

4.1 Population (base)

Patients aged 60 years or older, undergoing major elective non-cardiac surgery under general or spinal anesthesia are eligible for study participation. Major elective noncardiac surgery is defined as all noncardiac surgical procedures requiring an expected hospital admittance of ≥ 24 hours that have been preceded by a preoperative consultation at the anesthesia preoperative screening outpatient clinic. For patients who undergo surgery more than once, the first surgery will be included in the analysis. Reoperations will not be included.

4.2 Inclusion criteria

In order to be eligible to participate in this study, a subject must meet all of the following criteria:

- ≥ 60 years old;
- Major noncardiac surgery defined as all noncardiac surgical procedures requiring an expected hospital stay of at least 24 hours;
- Elective surgery, defined as surgery that has been preceded by a preoperative consultation at the anesthesia preoperative screening outpatient clinic.

4.3 Exclusion criteria

A potential subject who meets any of the following criteria will be excluded from participation in this study:

- Patients unable to fully comply to study needs (e.g. legally incapable patients or patients unable to communicate in Dutch or English).
- Patients with an American Society of Anesthesiologists (ASA) Physical status 5

4.4 Sample size calculation

For this study, we aim to include 500 patients at the UMCU in this study. A similar study will be conducted at the University Health Network Toronto (UHNT), Toronto, Canada and they will include 500 patients with the same in- and exclusion criteria. After including all patients in both centers, we will combine the data resulting in a total study population of 1,000 patients. In a previous conducted pilot study by the UHNT (registered at ClinicalTrial.gov: NCT02146560), 300 patients undergoing major elective noncardiac surgery were included and disability was assessed by the WHODAS 2.0 after 6 months. The incidence of troponin elevation in this pilot was 14.1%. We do however expect an incidence of 11.0% as patients included in the pilot were mainly vascular patients, who are more

prone to have postoperative troponin elevations⁴. The mean WHODAS 2.0 in patients with an elevation in troponin was 29% compared to 15% in patients without troponin elevation. Based on these results, and using a level of significance of 0.05 and a power of 0.8 we expect 104 patients with troponin elevation. As the ratio between troponin elevation and no troponin elevation is $0.89/0.11 = 8$, we need to include 832 patients. We expect a dropout of 20% (based on the number of patients who did not fill out the WHODAS 2.0 after 6 months in the pilot study), leading to a final sample size of approximately 1,000 patients.

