5. METHODS

5.1 Study parameters/endpoints

5.1.1 Main study parameter/endpoint

Disability is expressed by the WHODAS 2.0, which is based on difficulties experienced by the respondent in different functional domains including, cognition, mobility, self-care, getting along, life activities and participation during the previous 30 days. Disability is defined as a decrement in each functioning domain corresponding to score between 0% and 100%, in which no disability stands for a score of 0% and full disability represents a score of 100%, including death. The WHODAS 2.0 is easy to use and patient centered (see F1 for the questionnaire). In a validation study including noncardiac surgical patients, the WHODAS 2.0 has been found to be a clinically acceptable, valid, reliable and responsive instrument for measuring postoperative disability²⁷.

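### At the plan's own 1:8 ratio, no 0–100 score with means of 29 and 15 gives 104 PMI patients at 80% power; the stated power is probably too low, and none is stated for the phenotype comparison

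*Combined protocol and SAP*

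**What the plan says.** Section 4.4 (Sample size calculation) rests on a pilot: "The mean WHODAS 2.0 in patients with an elevation in troponin was 29% compared to 15% in patients without troponin elevation". From these means it states, "using a level of significance of 0.05 and a power of 0.8 we expect 104 patients with troponin elevation". It then applies the ratio: "As the ratio between troponin elevation and no troponin elevation is $0.89/0.11 = 8$, we need to include 832 patients". A 20% dropout brings the total to about 1,000, pooled over two centres. The incidence behind the ratio is the plan's own: "We do however expect an incidence of 11.0% as patients included in the pilot were mainly vascular patients". No SD, sidedness, test or allocation is given for the 104.

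Section 5.1.1 bounds the outcome: "no disability stands for a score of 0% and full disability represents a score of 100%, including death". Section 7.2 compares 6-month WHODAS 2.0 between patients with and without PMI by t-test or Mann-Whitney test, followed by adjusted linear regression. Section 2.1 sets a wider aim, to investigate and compare the effects of "different PMI phenotypes (myocardial infarction and NITE) and noncardiac MAPE on disability". No section gives power or precision for that comparison.

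**The concern.** A sample size for two means needs an SD. When it is missing, the reader can solve for the SD that the stated numbers imply and ask whether it is plausible. Here, at the ratio the plan uses, it is not even possible. The stated size and power therefore do not describe the planned comparison.

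Two things are at stake. The only power figure in the protocol cannot be checked and probably misstates the power for PMI versus no PMI. And because it is the only figure, it may be carried over to MI versus NITE, where far fewer patients contribute and where it does not apply.

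**Working it through.** **Inputs.** Means 29 and 15 (difference 14), alpha 0.05, power 0.80, 104 PMI patients, ratio 8, incidence 11%, dropout 20%, total 1,000 (all Section 4.4). Score range 0–100 with death at 100 (Section 5.1.1). MI about one third of PMI (Summary and Section 1). Two-sided alpha is assumed, so z = 1.960 + 0.842 = 2.802.

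**1. SD implied by the plan's figures.** SD = 14 / [2.802 × √(1/n1 + 1/n2)].
- 104 vs 832: 48.0
- 104 vs 728 (832 read as the total): 47.7
- One-sided alpha: 54.1 and 53.7

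**2. Largest possible SD.** For a score on 0–100 with mean m, the maximum is √[m(100 − m)].
- PMI: √(29 × 71) = 45.4
- No PMI: √(15 × 85) = 35.7
- Pooled at 1:8: √[(2059 + 8 × 1275)/9] = 36.9

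An SD of 48 exceeds all three.

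**3. Most PMI patients that 1:8 could need.** With both groups at their maximum and unequal variances, n1 = 2.802² × (2059 + 1275/8)/14² = 88.8, so 89. With the largest pooled SD (36.9) it is 62.

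**4. Other routes to 104.**
- Mann-Whitney efficiency of 0.955 or 0.864 lowers the implied SD to 47.0 or 44.7, still above the no-PMI and pooled limits.
- 29% and 15% read as proportions at 1:8 need 70 PMI patients (78 with continuity correction, 76 by arcsine).
- Equal groups, 104 vs 104: SD = 36.0, below the 1:1 pooled limit of √[(2059 + 1275)/2] = 40.8. This is attainable. With that SD, 104 vs 832 has 96% power.

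**5. Requirement at 1:8 for assumed SDs.** n1 = (2.802 × SD/14)² × (1 + 1/8), rounded up.

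| Assumed SD | PMI needed | Total before dropout |
|---|---|---|
| 20 | 19 | 171 |
| 25 | 29 | 261 |
| 35 | 56 | 504 |

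**6. Power at the expected completers.** 1,000 × 0.8 = 800 with a score; 800 × 0.11 = 88 PMI and 712 without. Power = Φ(14/SE − 1.96).

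| Assumed SD | 104 vs 832 | 88 vs 712 |
|---|---|---|
| 20 | >99.9% | >99.9% |
| 25 | >99.9% | 99.9% |
| 30 | 99.4% | 98.5% |
| 35 | 97.0% | 94.3% |
| 36 | 96.2% | 93.0% |
| Every score 0 or 100 (45.4 and 35.7) | 85.8% | 79.7% |

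**7. Phenotypes.** 88/3 = 29.3 MI and 58.7 NITE. Detectable difference at 80% power = 2.802 × SD × √(1/n1 + 1/n2).

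| Assumed SD | MI vs NITE | MI vs none (712) | NITE vs none (712) |
|---|---|---|---|
| 20 | 12.7 | 10.6 | 7.6 |
| 25 | 15.8 | 13.2 | 9.5 |
| 35 | 22.2 | 18.5 | 13.3 |

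At the 15% PMI incidence in the Summary (120 PMI: 40 MI, 80 NITE), the MI–NITE figures become 10.8, 13.6 and 19.0 points.

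**The case against.** The strongest reply is that Section 4.4 never says 104 was computed at 1:8. The 104 comes first and the ratio is applied afterwards, which fits an equal-group formula with an SD of about 36. This stands, and it limits the claim. A reader might infer that no WHODAS distribution with these means could give 104 at all; the documents do not support that, because the impossibility holds only at 1:8. (Reading 104 as the total of two equal groups of 52 gives an SD of 25.5, but the text calls all 104 patients troponin-positive.) The reply does not rescue the figure: 104 with 80% power would then belong to a 1:1 design that the study does not have.

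Second, the true SD is unknown, and scoring death as 100 widens the spread. A reader might infer that power is far above 80% whatever the SD. At 88 versus 712 it is 79.7% in the extreme case, so that reading fails too.

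Third, PMI versus no PMI is a legitimate primary contrast. The hypothesis in Section 1 concerns any troponin elevation, and Section 7.2 opens with that comparison. This stands: the phenotype gap is measured against Section 2.1, is separate from the arithmetic, and is secondary to it.

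Fourth, a reader might infer that a null MI–NITE result is to be presented as equal prognosis. No such claim is planned.

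Finally, the phenotype counts are soft. Section 1 gives PMI incidences of 11 to 19%, and Section 5.3 says high-sensitivity troponin doubles MI detection. Detectable differences should therefore be shown over a range of counts.

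**Conclusion.** The point holds for the 1:8 design. The 104 patients and 80% power cannot both describe it: the implied SD is 48 against limits of 45.4, 35.7 and 36.9 pooled, and at most 89 PMI patients are needed. This rests on the plan's means, its score range and a two-sided alpha; a one-sided alpha makes the conflict worse.

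It would be wrong to infer that PMI versus no PMI is underpowered. The likely error is understated power: at the expected 88 PMI completers it is 94% or more for assumed SDs of 20 to 35, about 93% at 36, and about 80% only if every score is 0 or 100.

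The primary objective's phenotype comparison has no stated precision. At 11% PMI and one third MI, the detectable MI–NITE difference of 12.7 to 22.2 points (assumed SDs 20 to 35) is close to or above the whole 14-point pilot difference. Section 4.4 should be corrected, but nothing here calls the sample size or the conduct of the study into question.

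**What to change.** Keep 1,000 patients and rewrite Section 4.4.

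1. State the pilot SD in each group with deaths scored 100, together with the test, sidedness and allocation used.
2. Replace the 104 and the 80% with the power for PMI versus no PMI at the expected completers (about 88 versus 712), and recompute the 832. As written, 104 × 8 = 832 is the no-PMI group, not the number to include.
3. Add detectable differences for MI versus NITE, MI versus none and NITE versus none, over a range of PMI incidences and MI shares.
4. State that the MI–NITE estimate will be reported with its confidence interval.

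The cost is one recalculation from pilot data and a rewritten section. No patients or procedures are added. The stated power for PMI versus no PMI probably rises, and the limited precision for the phenotypes becomes visible.

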7. STATISTICAL ANALYSIS

7.1 Data description

Baseline characteristics will be presented using percentages for categorical covariates, means with standard deviations and/or medians with interquartile ranges for continuous variables. Comparison between baseline characteristics will be done using the chi-square test for categorical variables and Student's t-test or Mann Whitney-U test for continuous variables as appropriate. Based on a pilot study conducted at UHNT, we assume a patient dropout of 20% at 6 months follow up (see Sample size calculation). Baseline characteristics of patients who did and did not respond at 6 months follow up will be compared to examine whether selective dropout occurred. Multiple imputation will be performed in case of any missing data. Throughout the analyses, a *p*-value of 0.05 is considered statistically significant.

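### Section 4.4 takes the number of patients without troponin elevation (832) as the total to include, and its 104 patients with elevation cannot be the 1:8 requirement for a 14-point difference

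*Combined protocol and SAP*

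**What the plan says.** All the steps are in section 4.4 (Sample size calculation) of the combined protocol and SAP.

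- Effect, from the pilot: "The mean WHODAS 2.0 in patients with an elevation in troponin was 29% compared to 15% in patients without troponin elevation".
- Incidence: the pilot had 14.1%, but the plan chooses a lower figure: "We do however expect an incidence of 11.0" per cent.
- Number with elevation: "using a level of significance of 0.05 and a power of 0.8 we expect 104 patients with troponin elevation".
- Ratio: the sentence beginning "As the ratio between troponin elevation and no troponin elevation is" gives 0.89/0.11 = 8, and from it "we need to include 832 patients".
- Dropout of 20% is then added, "leading to a final sample size of approximately 1,000 patients", to be shared between the two centres at 500 each.

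Section 4.4 states no SD, no sidedness and no formula. Section 5.1.1 puts the score on a 0–100 scale, where "full disability represents a score of 100%, including death". Section 7.1 repeats the dropout assumption ("we assume a patient dropout of 20% at 6 months follow up") and provides for multiple imputation. Section 7.2 plans a t-test or Mann-Whitney comparison of the 6-month score between patients with and without PMI.

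**The concern.** There are two faults in one calculation. First, a count for one group is carried forward as the whole cohort, and the final figure of about 1,000 is built on it. Second, the starting number, 104, comes without the inputs needed to check it, and it looks far too large for a 14-point difference on a 0–100 score.

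At stake is whether a reader can verify the stated 80% power, know how many patients with elevation to expect, or see what difference the study can detect. A reader who noticed only the first fault might also replace 832 with 936 and inflate for dropout (936/0.8 = 1,170), enlarging the study on the strength of an unsupported 104.

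**Working it through.** **Inputs from the documents.** Alpha 0.05, power 0.80, means 29 and 15 (difference 14), incidence 11.0%, 104 with elevation, dropout 20%, about 1,000 enrolled (all section 4.4); scale 0–100 (section 5.1.1); two-group comparison (section 7.2).

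**Assumptions.** A two-sided test, equal dropout in both groups, and SDs of 25, 30 and 36 for illustration. The documents give no SD.

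**1. Reproducing the plan's figures**
- 0.89/0.11 = 8.09, rounded to 8; 8 × 104 = 832. The arithmetic reproduces exactly.
- 832 × 1.2 = 998, about 1,000. Dividing by the retained fraction gives 832/0.8 = 1,040, so dropout was added as a multiplier of 1.2. This is a second, smaller slip.

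**2. What 832 counts**
- 0.89/0.11 is non-elevated per elevated, so 832 is the non-elevated group.
- Matching total: 104 + 832 = 936, or 104/0.11 = 945 unrounded.
- Elevated patients in a cohort of 832: 832 × 0.11 = 91.5, not 104.

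**3. Whether 104 can be the 1:8 requirement for 14 points**
- Two-sample t-test (noncentral t): the common SD that gives 80% power at 104 versus 832 is 48.0. A one-sided test would need 54.1.
- On a 0–100 scale with mean m, the SD cannot exceed √(m(100 − m)). That is √(29 × 71) = 45.4 in the elevated group and √(15 × 85) = 35.7 in the other.
- Largest pooled SD: √((104 × 29 × 71 + 832 × 15 × 85)/936) = 36.9, well below 48.0.
- Allowing unequal variances at those ceilings, n = ((1.96 + 0.84)/14)² × (2059 + 1275/8) ≈ 89 elevated patients, or 91 with a Welch t-test. Both are below 104.
- Treating 29% and 15% as proportions gives 70 elevated, or 78 with continuity correction. Neither is 104.

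**4. What 1,000 enrolled patients yield**
- 1,000 × 0.11 = 110 with elevation; 110 × 0.8 = 88 with an observed 6-month score.
- 800 − 88 = 712 without elevation.
- 104 observed needs an incidence of 104/800 = 13.0%. The pilot's 14.1% would give 800 × 0.141 = 113, and the 15% in the Summary would give 120.

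**5. Requirement, power and detectable difference** (two-sided 0.05)

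| Assumed common SD | Elevated needed at 1:8 for 14 points, 80% power (total) | Power for 14 points at 88 vs 712 | Detectable difference at 80% power, 88 vs 712 |
|---|---|---|---|
| 25 | 29 (261) | 99.9% | 7.9 |
| 30 | 41 (369) | 98.5% | 9.5 |
| 36 | 59 (531) | 93.0% | 11.4 |

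At the ceiling SDs (45.4 and 35.7), SE = √(2059/88 + 1275/712) = 5.02. Power is then 79.7% by the normal approximation and 78.9% by Welch.

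**The case against.** Four objections deserve an answer.

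*The 104 may not be a 1:8 figure.* Section 4.4 gives 104 first and applies the ratio afterwards; 104 per group with equal allocation fits an SD of about 36. That may be its origin, but the documents do not say. It would also confirm that 104 is not the requirement at the allocation the study will have.

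*The impossibility argument sets a common SD against group-specific limits, and a Mann-Whitney test is allowed.* The unequal-variance calculation answers the first part: at most 91 are needed. Dividing 89 or 91 by 0.864, the worst-case efficiency of Mann-Whitney, gives 103 or 105, which seems to rescue 104. It does not. That bound is for a location shift between distributions of the same shape, whereas the ceiling SDs arise only if every score is 0 or 100.

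*The 88 is a cautious figure.* Imputation and scoring deaths as 100 could raise the number analysed, up to 110, and a higher incidence would raise the number observed. This stands as a caveat. But imputed outcomes do not carry full information, section 4.4 itself treats dropouts as lost, and 11.0% is the plan's own choice.

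*Nothing much follows.* Power for 14 points is adequate at plausible SDs. That is right, and it limits the point to the justification. The reassurance covers only elevation versus no elevation, however. The primary objective also compares myocardial infarction, NITE and noncardiac MAPE, and the first two divide the elevated group further.

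**Conclusion.** The concern holds. 832 is the non-elevated count and is wrongly used as the total; with 104 elevated, the total would be 936 to 945. The 104 cannot be the 1:8 requirement for 14 points on this scale with these means, and that conclusion rests on no guessed SD. At the plan's own inputs, about 88 elevated and 712 non-elevated patients will have an observed outcome, assuming equal dropout in both groups and 500 patients from each centre.

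No loss of power for the 14-point two-group comparison is claimed. The sample-size justification should be corrected; the two-group comparison gives no reason to change the study size. The power figures of 93% or more depend on the assumed SDs of 25 to 36 and should be confirmed with the pilot SDs.

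**What to change.** Keep 1,000 patients and rewrite section 4.4:

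1. Stop using 832 as the total. If it is mentioned at all, label it as the non-elevated group that goes with 104.
2. Retrieve the SDs from the pilot. State them with the sidedness and the formula, and recompute the number with elevation from them. Carry neither 104 nor 936 forward as the requirement.
3. Replace the justification with wording such as: *With 1,000 patients, 11.0% incidence and 20% dropout, we expect about 88 patients with and 712 without troponin elevation to have an observed 6-month WHODAS 2.0. With pilot SDs of [x] and [y] and two-sided alpha 0.05, this gives [z]% power for a 14-point difference and a detectable difference of [d] points at 80% power.*
4. Add that multiple imputation and scoring death as 100% may raise the number analysed, and that the calculation does not rely on either.

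The cost is protocol wording and retrieval of the pilot SDs. No patients are added and the analysis does not change.
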